Adverse effects reported in > 20% to 100% of subjects treated with cetuximab include: nail changes, radiation recall, rash, itching, dry skin, acne, dehydration, weight loss, anorexia, mucositis, constipation, diarrhea, vomiting, nausea, insomnia, headache, fatigue, pain, fever, infection, cough, and dyspnea.

Adverse effects reported in 4% to 20% of subjects include: allergic reaction/hypersensitivity which may cause rash, hypotension, wheezing, shortness of breath, and swelling of the face or throat, confusion, depression, anxiety, syncope, sepsis, and pulmonary embolism.

Adverse effects that are rare and serious that occurred in 3% or less of subjects include: interstitial lung disease, renal failure, and cardiopulmonary arrest and/or sudden death.

Note: Cetuximab in combination with other agents could cause an exacerbation of any adverse event currently known to be caused by the other agent, or the combination may result in events never previously associated with either agent.

Additional information on common, serious, or severe reactions includes:

Infusion Reactions: In clinical trials, severe, potentially fatal infusion reactions were reported. These events included the rapid onset of airway obstruction (bronchospasm, stridor, and hoarseness), hypotension, shock, loss of consciousness, myocardial infarction, and/or cardiac arrest. Approximately 90% of severe infusion reactions occurred with the first infusion despite premedication with antihistamines.

Dermatologic Toxicity: In clinical studies of cetuximab, dermatologic toxicities, including acneiform rash, skin drying and fissuring, and inflammatory and infectious sequelae (e.g. blepharitis, conjunctivitis, keratitis, cheilitis, cellulitis, cyst), and hypertrichosis were reported. In patients with advanced colorectal cancer, acneiform rash was reported in 88% (560/633) of all treated patients, and was severe (Grade 3 or 4) in 12% (79/633) of these patients. Subsequent to the development of severe dermatologic toxicities, complications including *S. aureus* sepsis and abscesses requiring incision and drainage were reported.

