3.2 Irinotecan (Camptosar®) (NSC616348)

a. PHARMACOLOGY

Mechanism of Action: Irinotecan and its metabolite SN-38 inhibit topoisomerase I. Topoisomerase I relieves torsional strain in the DNA helix during replication and RNA transcription by inducing single-strand breaks. By binding with the topoisomerase I—DNA complex, irinotecan or SN-38 prevents the religation of the single-strand breaks. Irreversible DNA damage occurs when a DNA replication fork encounters the irinotecan or SN-38/topoisomerase I complexes resulting in double-strand DNA breaks. Camptothecins are highly S-phase specific in their activity due the requirement of DNA synthesis.

b. PHARMACOKINETICS

1. Absorption: N/A

2. Distribution: Protein binding of irinotecan is 30-70%, whereas SN-38 shows a higher protein binding of 95%. Both irinotecan and SN-38 are primarily bound to albumin. Volume of distribution of irinotecan is approximately 110-234 L/m².

3. Metabolism: Irinotecan is metabolized primarily in the liver by carboxylesterase to SN-38, and via hepatic cytochrome P450 (CYP) 3A4 to aminopentane carboxylic acid (APC). SN-38 is conjugated to form a glucuronide metabolite by the enzyme UDP-glucuronosyl transferase 1A1 (UGT1A1). Genetic polymorphisms exist in the enzyme UGT1A1, leading to different levels of exposure and toxicity among patients. In addition, both irinotecan and SN-38 undergo plasma hydrolysis between their active (lactone) and inactive forms (carboxylate). Finally, a small amount of irinotecan is metabolized by the intestinal wall.

4. Elimination: Approximately 10-25% of irinotecan is recovered unchanged in urine whereas only small amounts of SN-38 have been found. Clearance is approximately 13.5 L/hr/m². In addition, irinotecan has approximately 25% biliary excretion.

c. ADVERSE EFFECTS

1. Refer to the current FDA-approved package insert for the most comprehensive and up to date information on adverse reactions.

Adverse effects reported in > 20% to 100% of subjects treated with irinotecan include: diarrhea and cholinergic reaction (may be severe), constipation, nausea, vomiting, asthenia, infection, leukopenia, neutropenia, alopecia, anorexia, weight loss, anemia, fatigue, fever, pain, dizziness, cough, dyspnea, mucositis, rash, thrombocytopenia. Adverse effects reported in 4% to 20% of subjects include: gastrointestinal perforation, hypersensitivity reaction, cardiovascular events, thromboembolic events, interstitial lung disease.

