3.3 Vemurafenib (Zelboraf®) (NSC-761431) (IND-122167)

a. PHARMACOLOGY

Mechanism of Action: Inhibitor of mutated forms of the BRAF serine-threonine kinase enzyme, including BRAF V600E, exhibiting anti-tumor effects in melanomas with mutated BRAF V600E. BRAF gene mutations may lead to cell proliferation in the absence of growth factors.

b. PHARMACOKINETICS

1. Absorption: Time to peak ~3 hours
2. Distribution: $V_d \sim 106L$, >99% protein binding
3. Metabolism: Not appreciably metabolized in humans, however CYP3A4 was the primary enzyme responsible for the metabolism of vemurafenib. Unchanged vemurafenib was the major component detected in plasma samples following oral administration.
4. Elimination: Feces (94%) & urine (1%), half life elimination 57 hours (30-120 hour range)

c. ADVERSE EFFECTS

1. Adverse Effects:

Adverse Events with Possible Relationship to Vemurafenib		
Likely (>20%)	Less Likely (4 – ≤20%)	Rare but Serious (≤3%)
CARDIAC DISORDERS		
	Peripheral Edema	Atrial fibrillation Hypotension Prolonged QT interval Retinal vein occlusion Vasculitis
EYE DISORDERS		
		Photosensitivity Photophobia Blurred vision Uveitis
GASTROINTESTINAL DISORDERS		
Nausea Diarrhea Vomiting	Decreased appetite Constipation Dysgeusia	Colonic polyps
GENERAL DISORDERS AND ADMINISTRATION SITE CONDITIONS		
Fatigue Headache		
HEPATOBIILIARY DISORDERS		
	Increased gamma-glutamyl transferase	Increased serum alkaline phosphatase Increased serum ALT Increased serum AST Increased serum bilirubin
IMMUNE SYSTEM DISORDERS		
	Allergic Reaction	Anaphylaxis Hypersensitivity Reactions
METABOLISM AND NUTRITION DISORDERS		
		Weight loss
MUSCULOSKELETAL AND CONNECTIVE TISSURE DISORDERS		
Arthralgia Myalgia	Limb pain Back pain Musculoskeletal pain weakness	Arthritis

NERVOUS SYSTEM DISORDERS		
		Cranial nerve palsy (facial) Dizziness Peripheral neuropathy
RENAL AND URINARY DISORDERS		
		Increased serum creatinine
RESPIRATORY, THORACIC AND MEDIASTINAL DISORDERS		
	Cough	
SKIN AND SUBCUTANEOUS TISSUE DISORDERS		
Alopecia Pruritus Skin photosensitivity Rash Hyperkeratosis Skin neoplasm Squamous cell carcinoma of skin	Maculopapular rash Xeroderma Sunburn Erythema Papular rash	Malignant melanoma(new primary) Stevens-Johnson syndrome Toxic Epidermal Necrosis

QT Prolongation: Vemurafenib has been shown to increase the QT interval, leading to ventricular arrhythmias including Torsade de Pointes. Use with caution in patients who are taking concurrent QT prolonging medications or products.

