8.2 General Considerations

- a. Where several toxicities with different grades or severity occur at the same time, the dose modification applied should be the greatest reduction applicable.
- b. The maximum dose delay for any reason is 3 weeks.
- c. Doses omitted during a cycle will not be made up.
- d. If treating investigator feels an event is attributable to another drug, then, after conversation with the Study Chair, other modification may be considered.
- e. Patient may continue protocol treatment if either cetuximab or irinotecan must be stopped. If patient must stop vemurafenib treatment, patient should be removed from all protocol treatment.
- f. Advise patients to avoid sun exposure while on treatment with vemurafenib and cetuximab. Encourage patients to wear protective clothing and to use a broad spectrum UVA/UVB sunscreen and lip balm (SPF \geq 30) when outdoors.

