* G-CSF or pegylated G-CSF may be utilized per ASCO guidelines (<http://jop.ascopubs.org/cgi/content/full/2/4/196>).

e. Thrombocytopenia

Toxicity Grade	Dose Modification
2	Hold irinotecan until recovery to \leq Grade 1. Resume at same dose level.
3 or 4	Hold all treatment until recovery to \leq Grade 1. Reduce irinotecan by one dose level.

f. Blood Bilirubin Increased

Toxicity Grade	Dose Modification
2	Hold irinotecan until recovery to \leq Grade 1. Resume at same dose level.
3 or 4	Hold irinotecan and vemurafenib until recovery to \leq Grade 1. Reduce irinotecan and vemurafenib each by one dose level.

g. Mucositis

Toxicity Grade	Dose Modification
2	Hold irinotecan until recovery to \leq Grade 1. Resume at same dose level.
3 or 4	Hold all treatment until recovery to \leq Grade 1. Reduce irinotecan by one dose level.

h. Fatigue

Toxicity Grade	Dose Modification	
	Arm 1	Arm 2
2	Hold all treatment until recovery to \leq Grade 1. Resume at same dose level.	Hold all treatment until recovery to \leq Grade 1. Resume at same dose level.
3 or 4	Hold all treatment until recovery to \leq Grade 1. Reduce irinotecan by one dose level.	Hold all treatment until recovery to \leq Grade 1. At the first occurrence, reduce irinotecan by one dose level. At the second occurrence, reduce vemurafenib by one dose level. At third occurrence, reduce irinotecan by one dose level. At the fourth occurrence, the patient must be removed from protocol treatment.

i. Arthralgia

Toxicity Grade	Vemurafenib Dose Modification
2	Hold vemurafenib until recovery to \leq Grade 1. Resume at same dose level.
3 or 4	Hold vemurafenib until recovery to \leq Grade 1. Reduce vemurafenib by one dose level.

j. Pneumonitis

Toxicity Grade	Cetuximab Dose Modification
2	Hold cetuximab until recovery to \leq Grade 1. Resume at same dose level.
3 or 4	Hold cetuximab until recovery to \leq Grade 1 and interstitial lung disease has been ruled out. Reduce cetuximab by one dose level. Discontinue protocol treatment if interstitial lung disease is confirmed by CT scan.

k. Rash

Toxicity Grade	Dose Modification	
	Arm 1	Arm 2 + Arm 3

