Toxicity Grade	Dose Modification
1 or 2	Supplementation with magnesium. Closely monitor patient for appropriate magnesium levels.
3 or 4	Institute maximal medical management with magnesium. If Grade \geq 3 persists despite magnesium supplementation, reduce cetuximab by one dose level. At second occurrence, discontinue cetuximab therapy.

r. Other non-hematologic toxicities

Toxicity Grade	Dose Modification
3 or 4	Hold all treatment and monitor toxicity at least weekly. If toxicity resolves to \leq Grade 1 within 3 weeks, reduce irinotecan by one dose level and resume treatment.

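### At Grade 3–4 pneumonitis, Section 8.3j holds only cetuximab while interstitial lung disease is ruled out and gives no instruction for irinotecan, for which Section 3.2c also lists that disease

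*Combined protocol and SAP*

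**What the plan says.** The pneumonitis table in Section 8.3j has a single action column, headed "Cetuximab Dose Modification". Its Grade 3 or 4 row holds cetuximab until recovery to Grade 1 or less and until "interstitial lung disease has been ruled out. Reduce cetuximab by one dose level. Discontinue protocol treatment if interstitial lung disease is confirmed by CT scan". Irinotecan is not mentioned, and no deadline is set for the CT.

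Both infused drugs carry ILD in the protocol's own lists. For irinotecan, Section 3.2c states: "Adverse effects reported in 4% to 20% of subjects include: gastrointestinal perforation, hypersensitivity reaction, cardiovascular events, thromboembolic events, interstitial lung disease". For cetuximab, Section 3.1c puts ILD in its rare-and-serious band of 3% or less: "interstitial lung disease, renal failure, and cardiopulmonary arrest and/or sudden death". For vemurafenib, the Section 3.3c table has only cough under "RESPIRATORY, THORACIC AND MEDIASTINAL DISORDERS".

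A Grade 3–4 non-hematologic toxicity without a row of its own falls under Section 8.3r, which begins: "Hold all treatment and monitor toxicity at least weekly". That row then allows resumption, with irinotecan reduced one level, if the event resolves to Grade 1 or less within 3 weeks.

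**The concern.** The row treats ILD as serious enough that confirmation stops every drug, and it requires ILD to be excluded before cetuximab restarts. During that work-up, though, it acts on only one of the two drugs for which the protocol lists ILD. A site that follows the table literally could give irinotecan on its due day with the ILD question unanswered. Irinotecan is part of all three arms, so this is a patient-safety matter throughout the trial. It does not bear on the primary analysis.

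**Working it through.** The plan has no figure of its own to reproduce here. The check is a comparison of rules, followed by a count of doses.

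**1. Row j against the default, at Grade 3–4**

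| Element | 8.3j (pneumonitis) | 8.3r (default) |
|---|---|---|
| Drugs held during work-up | cetuximab | all |
| ILD must be excluded before resuming | yes, for cetuximab | no |
| Stop all treatment if ILD is confirmed | yes | no such rule |
| Drug reduced on resumption | cetuximab | irinotecan |

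Row j is weaker on the first line and stricter on the second and third.

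**2. Does another rule hold irinotecan?**

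- Section 8.2a: "Where several toxicities with different grades or severity occur at the same time, the dose modification applied should be the greatest reduction applicable". This operates only when toxicities coincide. Dyspnea and cough are listed for irinotecan in 3.2c and have no row in 8.3, so at Grade 3–4 they would fall under 8.3r and support holding everything. Grade 3–4 fatigue would do the same through 8.3h.
- Section 8.2d permits another modification if the investigator attributes the event to a different drug and has spoken with the Study Chair. This is discretionary.
- Section 8.2e lets treatment continue when cetuximab has to stop, which fits reading row j as leaving irinotecan on schedule.
- Section 7.6 allows removal for unacceptable toxicity, which is a judgment.

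None of these requires an irinotecan hold when pneumonitis is the only qualifying Grade 3–4 toxicity.

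**3. How many doses?**

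Inputs: cetuximab and irinotecan both on days 1 and 15 of a 28-day cycle (7.2, 7.3, 7.5b), so the interval is 28/2 = 14 days; and Section 8.2b: "The maximum dose delay for any reason is 3 weeks", that is 3 × 7 = 21 days.

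Let t be the days from onset to the next dose day and c the days from onset to the CT result. Irinotecan doses falling due with ILD still open:

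- c ≤ t: none.
- t < c ≤ t + 14: one, at 100 mg/m² (level −3) to 180 mg/m² (starting dose) per 8.3a.
- c > t + 14: two. This needs a CT still unread 14 days after the first held cetuximab dose. A third would fall 28 days after that dose, beyond the 21-day limit.

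For a Grade 3–4 lung event, zero or one is the realistic range.

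**4. Is row j unusual?**

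Section 8.3 has 17 toxicity rows (b to r); leaving out p, which is ungraded, gives 16. At Grade 3–4, nine hold irinotecan (b, c, d, e, f, g, h, l, r) and seven do not (i, j, k, m, n, o, q). Three of the seven (j, k, n) concern an effect that 3.2c names for irinotecan. Row j is the only one of the 16 that makes resumption depend on excluding a diagnosis.

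**5. Size of one omitted dose**

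Using the Section 11.2 medians and 30.44 days per month:

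- Arm 1: 2.4 × 30.44 = 73 days. Doses fall due on days 1, 15, 29, 43, 57 and 71, which is 6; 1/6 = 17%.
- Arm 2: 4.8 × 30.44 = 146 days. Doses fall due on days 1 to 141 in steps of 14, which is 11; 1/11 = 9%.

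**The case against.** The strongest reply is that row j is a deliberate, disease-specific rule and that single-drug rows are this protocol's convention. Row j contains two ILD safeguards that 8.3r lacks, and Section 5.2a.12 already excludes patients with interstitial pneumonia or extensive symptomatic fibrosis at entry. A patient with Grade 3–4 pneumonitis will often also have Grade 3–4 dyspnea or cough recorded, and 8.2a with 8.3r then points to a full hold. Most clinicians would in any case wait for the CT. All of this stands. It narrows the gap to pneumonitis with no other qualifying toxicity recorded, but it does not supply an instruction for that case.

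Three stronger readings are tempting, and the documents do not support them.

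- A reader might infer that having its own row leaves pneumonitis less protected overall than the default. That is true only of the interim hold.
- A reader might infer an exposure of two doses (2 × 100 = 200 to 2 × 180 = 360 mg/m²). That needs a CT unread for 14 days after the first held cetuximab dose, or it counts recovery time after ILD has been excluded, when the stated hazard has passed.
- A reader might conclude that irinotecan should stay held until recovery to Grade 1 or less. This exceeds the harm identified. In Arm 1 it would keep both drugs off, so slow recovery without ILD could exceed the 3-week limit in 7.6, and 5.3a would then deny crossover because the patient left treatment for a reason other than progression.

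**Conclusion.** The point holds in a limited form. For Grade 3–4 pneumonitis with no other qualifying Grade 3–4 toxicity recorded, the plan as written allows a scheduled irinotecan dose, realistically zero or one, while ILD is unresolved. This is a cheap safety improvement to one row; it does not show that the dose-modification scheme is unsound.

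The conclusion rests on three things. Continued irinotecan is inferred from the row naming only cetuximab; no sentence orders it. Section 8.4 was not available to check and is assumed to hold no contrary instruction. The frequency of the situation is unknown: the 4% to 20% band in 3.2c is a listing for ILD under irinotecan, and reading it as a rate of Grade 3–4 pneumonitis in this trial would go beyond the documents.

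**What to change.** In the Grade 3 or 4 row of 8.3j, add: *Hold irinotecan as well until interstitial lung disease has been ruled out by CT.* Keep the cetuximab hold to Grade 1 or less, the cetuximab reduction, and the end of all protocol treatment on confirmed ILD. Leave the Grade 2 row and vemurafenib as they are.

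The change needs no new procedure. Its clinical costs are modest:

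- Usually at most one irinotecan dose is omitted and, under 8.2c, not made up.
- In Arms 2 and 3, vemurafenib is given alone for that interval. Section 2.0 reports one response in 21 patients on the BRAF inhibitor alone (1/21 = 4.8%).
- In Arm 1, both drugs are off until the CT is read. Because the irinotecan hold ends once ILD is excluded, the added risk of a delay over 3 weeks and of lost crossover is small.

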8.5 Adverse Event Reporting

Toxicities (including suspected reactions) that meet the expedited reporting criteria as outlined in [Section 16.0](#) of the protocol must be reported to the Operations Office, Study Chair and NCI via CTEP-AERS, and to the IRB per local IRB requirements.

9.0 STUDY CALENDAR

CLOSED EFFECTIVE 04/01/2016

9.1 Arm 1: Cetuximab + Irinotecan

REQUIRED STUDIES	Step 1 Initial Reg	Step 2 Rand	Cycle 1				Cycle 2				Cycle 3				Cycle 4				Ω FU prior to prog	% α FU after prog
			W 1	W 2	W 3	W 4	W 5	W 6	W 7	W 8	W 9	W 10	W 11	W 12	W 13	W 14	W 15	W 16		
PHYSICAL ∑																				
History and Physical Exam		X	X		X		X		X		X		X		X		X		X	X
Weight and Performance Status		X	X		X		X		X		X		X		X		X		X	X
Toxicity Notation					X		X		X		X		X		X		X		X	X
Disease Assessment		X									X								X	X
LABORATORY ∑																				
CBC/Differential/Platelets		X			X		X		X		X		X		X		X			
AST and ALT		X			X		X		X		X		X		X		X			
Serum creatinine/ Calculated creatinine clearance		X			X		X		X		X		X		X		X			
Total bilirubin		X			X		X		X		X		X		X		X			
Magnesium/ Potassium Calcium/Sodium/Bicarb/ Chloride		X			X		X		X		X		X		X		X			
SPECIMEN SUBMISSION																				
Tissue for BRAF Testing & Banking £	X																			
Blood £	X										X								X	X
Fresh Tissue Biopsy ζ		X																		
X-RAYS AND SCANS																				
CT or MRI for Disease Assessment ◇		X									X								X	X
ECG		X																		
TREATMENT ∑																				
Cetuximab			X		X		X		X		X		X		X		X			
Irinotecan			X		X		X		X		X		X		X		X			

Click here for [footnotes](#).

9.2 Arm 2: Cetuximab + Irinotecan + Vemurafenib

REQUIRED STUDIES	Step 1 Initial Reg	Step 2 Rand	Cycle 1				Cycle 2				Cycle 3				Cycle 4				Ω FU prior to prog	% FU after prog
			W 1	W 2	W 3	W 4	W 5	W 6	W 7	W 8	W 9	W 10	W 11	W 12	W 13	W 14	W 15	W 16		
PHYSICAL ∑																				
History and Physical Exam		X ¥	X		X		X		X		X		X		X		X		X	
Weight and Performance Status		X	X		X		X		X		X		X		X		X		X	
Toxicity Notation					X		X		X		X		X		X		X		X	
Disease Assessment		X												X					X	
Dermatologic evaluation ~		X					X							X					X	
Head and Neck Exam †		X					X							X					X	
LABORATORY ∑																				
CBC/Differential/Platelets		X			X		X		X		X		X		X		X			
AST and ALT		X			X		X		X		X		X		X		X			
Serum creatinine/ Calculated creatinine clearance		X			X		X		X		X		X		X		X			
Total bilirubin		X			X		X		X		X		X		X		X			
Magnesium/ Potassium Calcium/Sodium/Bicarb/Chlo ride		X			X		X		X		X		X		X		X			
SPECIMEN SUBMISSION																				
Tissue for BRAF Testing & Banking £	X																			
Blood £	X										X								X	X
Fresh Tissue Biopsy ¯		X																		
X-RAYS AND SCANS																				
CT or MRI ◇ ϖ		X									X								X	X
ECG ø		X			X				X				X							
TREATMENT ∑																				
Cetuximab			X		X		X		X		X		X		X		X			
Irinotecan			X		X		X		X		X		X		X		X			
Vemurafenib			X	X	X	X	X	X	X	X	X	X	X	X	X	X	X	X	X	X

Click here for [footnotes](#).

9.3 Arm 3: Cetuximab + Irinotecan + Vemurafenib

REQUIRED STUDIES	Step 3 Cross- over Reg	Cycle 1				Cycle 2				Cycle 3				Cycle 4				Ω FU prior to Prog	% FU after Prog
		W	W	W	W	W	W	W	W	W	W	W	W	W	W	W	W		
		1	2	3	4	5	6	7	8	9	10	11	12	13	14	15	16		
PHYSICAL ∑																			
History and Physical Exam	X ‡	X		X		X		X		X		X		X		X		X	X
Weight and Performance Status	X	X		X		X		X		X		X		X		X		X	X
Toxicity Notation				X		X		X		X		X		X		X		X	X
Disease Assessment	X									X								X	X
Dermatologic evaluation ~	X					X								X					X
Head and Neck Exam †	X					X								X					X
LABORATORY ∑																			
CBC/Differential/Platelets	X			X		X		X		X		X		X		X			
AST and ALT	X			X		X		X		X		X		X		X			
Serum creatinine/ Calculated creatinine clearance	X			X		X		X		X		X		X		X			
Total bilirubin	X			X		X		X		X		X		X		X			
Magnesium/ Potassium Calcium/Sodium/Bicarb/Chlo ride	X			X		X		X		X		X		X		X			
SPECIMEN SUBMISSION																			
Tissue for BRAF Testing & Banking £																			
Blood £	X									X								X	X
X-RAYS AND SCANS																			
CT or MRI ◊ ☞	X									X								X	X
ECG ♂				X				X				X							
TREATMENT ∑																			
Cetuximab		X		X		X		X		X		X		X		X			
Irinotecan		X		X		X		X		X		X		X		X			
Vemurafenib		X	X	X	X	X	X	X	X	X	X	X	X	X	X	X	X		

Click here for [footnotes](#).

Calendar 9.1, 9.2 and 9.3 footnotes.

- Σ Protocol treatment and parameters will continue at these intervals until progression of disease or until patient has met any of the guidelines in [Section 7.6](#).
- Ω After off treatment prior to disease progression, scans for disease assessment and physical assessments (with lab tests performed at the discretion of the treating investigator) should take place every 8 weeks until progression.
- % After off treatment following disease progression, physical assessments (with lab tests performed at the discretion of the treating investigator) should take place every 6 months for three years from the time of registration to Step 2.
- ¥ Must be done within 28 days prior to registration
- £ Required specimen submission for patients. See [Section 15.1](#) and [15.2](#) for additional information.
- ◇ CT or MRI for disease assessment must be performed every 8 weeks while on study treatment.
- α Patients who progress on Arm 1 may crossover to Arm 3 treatment if criteria in Section 5.3 are met and patient is registered to Step 3 Crossover Registration.
- δ Performed once every cycle for the first three cycles and every 3 cycles thereafter until 6 months after off treatment of vemurafenib. Anytime a dose adjustment is required for QTc changes, monitoring frequency is performed as if the patient just started treatment.
- ~ Performed at Step 2 Randomization or Step 3 Crossover Registration, after 4 weeks and every 2 months through 6 months after discontinuation of vemurafenib to evaluate for cutaneous malignancies (see [Section 8.3p](#)).
- ⊖ Chest imaging should be performed for disease assessment at baseline and with each restaging through 6 months after off treatment. This imaging will also allow for surveillance for non-cutaneous squamous cell carcinoma.
- † Performed at Step 2 Randomization or Step 3 Crossover Registration, after 4 weeks and every 2 months through 6 months after discontinuation of vemurafenib to evaluate for non-cutaneous SCC. (see [Section 8.3p](#)). The minimum criteria should be visual inspection of the oral mucosa and lymph node palpation performed by the treating physician.
- ∩ Only for sites listed in [Section 15.4](#).

